6.2 Potential Benefits

Participants in the control group may benefit from receiving educational information related to falls and alcohol use.

Participants in the intervention group may benefit from the intervention components of the study. They may gain strength from weekly exercises, which may put them at lower risk for experiencing a fall. Participants may benefit from discussing their experiences related to falls and alcohol use with other peers during weekly virtual group meetings, and participants may benefit from discussing their experiences with falls and alcohol use with an occupational therapist member of the research team during the weekly phone check-ins.

6.3 Analysis of Risks in Relation to Benefits

The principal risks of this study are loss of confidentiality and psychological stress. We will take an abundance of caution to protect the confidentiality of participants, and participants will be reminded of best practices prior to each weekly virtual group session. Participants will be provided various opportunities to discuss psychological distress with trained study staff and physician investigators. These risks are outweighed by the potential benefits that participants may receive from the intervention.

Participants who are assigned to the control arm may benefit from the provided educational materials.

Participants who are assigned to the intervention arm may benefit from weekly virtual group sessions and phone check-ins. These sessions will provide participants with the opportunity to discuss challenges

related to falls and alcohol use and ideas for overcoming these challenge. During preliminary qualitative research, Boston ARCH 4F participants expressed that group meetings and individual check-ins would be beneficial. Additionally, the home exercises may improve strength and balance in the participants. Furthermore, this intervention is tailored to address fall risk and alcohol use in this specific population, and it has the potential to reduce falls among PLWH who use alcohol more than a traditional fall prevention program.

The benefits outweigh the risks.

7 Study Subject Selection

- 7.1 Subject Inclusion Criteria
 - Male or female at least 18 years old
 - Prior or current participant in the Boston ARCH 4F Cohort
 - Any alcohol consumption in the last 30 days using Addiction Severity Index
 - Deemed a Fall Risk using the CDC STEADI Fall Risk Assessment Form¹⁹
 - Has reliable access to a phone or computer with internet connection

7.2 Subject Exclusion Criteria

• Requires wheelchair for mobility

8 Study Procedures

8.1 Recruitment- Up to 50 participants will be recruited to the Fall Prevention Pilot study from the Boston ARCH 4F Study cohort. To identify potentially eligible participants, the Boston University Medical Campus (BUMC) Biostatistics and Epidemiology Data Analytics Center (BEDAC) will generate a list of potentially eligible participants from the Boston ARCH 4F cohort who previously (at prior Boston ARCH 4F Study cohort assessments) endorsed alcohol use and fall history based on responses to the Addiction Severity Index (ASI) and the AIDS Clinical Trials Group (ACTG) Fall History Questionnaire.^{20–22} Participants who have not provided their written informed consent to be contacted about other research studies will be excluded from this list. Research assistants (RAs) and the research coordinator (RC) approach participants on this list for phone screening.

8.2 Phone Screening of Eligibility -The RAs and RC will reach out to Boston ARCH 4F participants who have been identified as potentially eligible based on the criteria described above. Participants interested in the study, if they agree, will be screened over the phone by interview/questionnaire for eligibility. If the participant meets all inclusion criteria and does not meet any exclusion criteria, they will be offered participation in the Boston ARCH 4F Fall Prevention Intervention Pilot Study. All eligible participants will be informed about the study and their written consent will be sought.

8.3 Baseline Assessment - Enrolled participants will complete a baseline research interview (a series of questionnaires to assess fall history and efficacy, substance use, prescription medications, physical and social environment, food security, and frailty) and physical assessments (physical function measures

including grip strength, short physical performance battery, and vision acuity) in-person at BUMC with an RA or RC. Additionally, an occupational therapist member of the study team will conduct the Canadian Occupational Performance Measure to assess the participant's exercise-related skills, needs, and goals.

If a participant's baseline is scheduled to occur more than 2 weeks (14 days) after the initial screening questionnaire was administered, an RA or RC will re-administer the screening questionnaire with the participant to confirm eligibility prior to conducting informed consent and the baseline research interview. The RA will re-administer the screening questionnaire within 24 hours prior to the scheduled baseline assessment. If the participant does not meet eligibility criteria based on the re-administered screening questionnaire assessment, then the participant is ineligible for the study, and they will be instructed to not attend their scheduled baseline assessment. However, if the RA is unable to get in touch with the participant prior to the scheduled baseline assessment, and the participant arrives at BUMC campus for the assessment, then the RA may re-administer the screening questionnaire inperson. If the participant does not meet eligibility criteria based on the re-administered screening questionnaire inperson. If the participant does not meet eligibility criteria based on the re-administered screening questionnaire inperson. If the participant does not meet eligibility criteria based on the re-administered screening questionnaire inperson. If the participant does not meet eligibility criteria based on the re-administered screening questionnaire assessment, then the participant is ineligible for the study, the baseline questionnaire will not be administered, and the participant will be compensated \$15 for their time.

If the participant's baseline research interview is scheduled within 2 weeks (14 days) after the initial screening questionnaire was administered, the RA or RC will not re-administer the screening questionnaire prior to completing the informed consent and the baseline research interview. However, if a participant reports no past 30 day alcohol use during the baseline research interview, the participant will be considered ineligible for the study and will not be randomized to either the intervention or control arm of the Fall Prevention Pilot, and no further follow-up will occur with the participant unless he or she is re-screened and determined eligible at a later date. The participant will still, however, be compensated for the baseline research study visit.

At the end of the baseline assessment, the RAs or RC will inquire about the participant's general availability, which will be used to identify the times during which the intervention's weekly group checkins will be held and determine whether the participant will be randomized. A participant will not be randomized if they have limited availability that cannot be accommodated. This decision will be made on a case-by-case basis. Additionally, after the baseline assessment has been administered, the RAs or RC will provide participants with technological assistance that may be helpful prior to the intervention. Although not all participants who complete a baseline assessment will be randomized to the intervention. Therefore, the RAs or RC will utilize this in-person time point to provide technological assistance with Zoom, such as setting up the Zoom app on a personal cell phone or computer, demonstrating the process of calling into a Zoom conference room (with or without the Zoom app), and identifying Zoom features that may be beneficial to understand (such as turning video and audio on and off). This technological assistance will be completely voluntary. Study staff will remind participants that they will only use Zoom during the Fall Prevention Pilot study if they are assigned to the intervention arm.

The baseline assessment will take approximately 2 hours to complete.

8.4 Intervention Arm Assignment/Randomization

Randomization: Once at least 6 participants have completed the baseline assessment, which we expect to occur between 2 and 4 weeks after study staff administer the first participant's baseline assessment, they will be randomized to either the intervention or control group using an automatic REDCap randomization module. These participants will be randomized in the "first wave" to either the intervention or control group using a 1:1 ratio on the factor of sex. The "first wave" of participants will be informed of their randomization assignment by study staff via phone call and will proceed with their assignment within the next week. After the "first wave" of participants are randomized, study staff will continue to screen and conduct baseline assessments for randomization in the "second wave" (similar to the first wave, the second wave will aim for n of at least 6). It will be acceptable for recruitment to occur over multiple randomization waves until recruitment goals have been met (to reach n=40 randomized participants). Procedures for subsequent recruitment wave(s) will be conducted in the same manner as the first wave. Participants will be randomized and informed of their randomization assignment after the baseline assessments for that wave have been conducted, which we expect to occur between 2 and 4 weeks after study staff administer the first baseline assessment of each subsequent wave.

In the event that study staff determine that the availability provided by a participant at baseline is too limited and cannot be accommodated (e.g., matched with other participants' availability so that two weekly group meeting days/times can be identified), that participant will not be randomized. This procedure is in place because a participant's limited availability will impact the participant's ability to participate in an entire component of the intervention (weekly virtual group meetings). During the subsequent wave(s) of recruitment and baseline assessments, study staff may re-contact participants who were enrolled in the Fall Prevention Pilot during a previous recruitment wave but were not randomized to a study arm due to limited availability at the time of the previous recruitment wave. Any participants who are re-contacted and provide an increased level of availability that study staff believe can be accommodated (e.g., matched with other participants' availability so that two weekly group meeting days/times can be identified) may be randomized during a subsequent wave(s). This will be determined on a case-by-case basis.

8.5 Control Arm Assignment

Participants who are assigned to the control arm will be informed of their assignment via phone call. Study staff will explain that being in the control group means that they will be receiving educational materials on fall prevention and alcohol use. The participant's mailing address will be confirmed, and the educational materials will be mailed by certified mail (or emailed, depending on participant preference) participant preference) the educational materials.

to their preferred address. The educational materials will only be mailed once, unless the participant misplaces the educational materials and requests to have study staff re-mail (or re-email, depending on

Intervention Arm Assignment: Participants who are assigned to the intervention arm will be informed of their assignment via phone call. Study staff will explain that being in the intervention group means that they will be participating in a 10-week intervention, which includes weekly home-based exercises, a weekly phone check-in, and weekly virtual group sessions. During this phone call, study staff will also obtain detailed availability from each participant, which will be used to schedule the weekly virtual group sessions.

8.6 Scheduling

Virtual Group Session: Virtual group session scheduling will occur in waves that align with the waves of randomization. After the "first wave" of randomization has occurred, study staff will reach out to all participants (at least 3) who have been assigned to the intervention arm to request days and times at which they are available and/or unavailable to participate in study activities. This availability will be used to help study staff identify the time slots in which the weekly virtual group sessions will be held. Once time slots for weekly virtual group sessions have been identified (up to two time slots), study staff will reach out to participants via phone call to schedule each participant for one of the two weekly virtual group sessions. Study staff will aim to assign an equal number of participants to each weekly virtual group session time slot; however, an equal allocation of participants to each group is not required. An unequal number of participants may be assigned to each group, provided that there are at least 3 participants assigned to the smallest group. Furthermore, study staff may also choose to assign all participants to one weekly virtual group session time slot if all participants' availability aligns with the same time slot or if having two groups would not allow for the minimum required number of participants (at least 3 per group). Procedures for scheduling the two additional weekly virtual group sessions for the subsequent wave(s) of randomized participants will be conducted in the same manner as the "first wave" of randomized participants.

Phone Check-in: Participants will be scheduled for their initial phone check-in when study staff contact the participants via phone call to schedule the participants for one of the two weekly virtual group sessions. The first phone check-in will be scheduled to occur between the first and second weekly virtual group sessions. During each weekly phone check-in, study staff will schedule the participant for the next week's phone check-in.

Conflicts and Rescheduling: If a participant experiences a scheduling conflict with a scheduled group session, they will miss that visit. Study staff will inquire about the upcoming week during a participant's weekly phone check-ins. Participants who indicate that they will have a scheduling conflict with their assigned weekly virtual group session time will be offered participation in the other group for that week only. Further, if a participant experiences a scheduling change that causes them to be unavailable for

either of the 2 group sessions, the participant will miss the group meetings. However, the participant will to continue to participate in the intervention by attending the weekly phone check-ins and conducting the weekly exercise assignments, and participants will be encouraged to attend future virtual group meetings if they experience a schedule change that allows for their attendance. The weekly virtual group meeting sessions will be combined into one session if weekly participation drops below 3 participants per session for at least two consecutive weeks.

8.7 Educational Component (Control Group Only)

Fall Prevention and Alcohol Use Educational Materials: The RAs and RC will call participants to inform them that they have been randomly assigned to the control group, and as a result they will be receiving educational materials about fall prevention and alcohol use. The RAs and RC will provide the participant with a brief overview of the educational materials that they will receive. The educational materials will be sent to the participant by certified mail (or by email, if this is the participant's preferred method) within one week of being informed of their randomization arm assignment. The educational materials will only be mailed once, unless the participant misplaces the educational materials and requests to have study staff re-mail (or re-email, depending on participant preference) the educational materials.

8.8 Intervention Process (Intervention Group Only)

Note: None of the below research activities will be recorded (audio or visual).

Virtual Group Session via Video/Phone: Weekly virtual group sessions will be held at up to two time points each week. Participants will be assigned to one of up to two time points and will be asked to attend the virtual group session for about 30 minutes each week for 10 weeks. The weekly virtual group sessions will be led by a licensed occupational therapist member of the study team, who is trained in group facilitation via Zoom. RAs will help coordinate and schedule the sessions with participants. Participants will have the option of using video or phone to participate (use of video will be encouraged). If two groups were scheduled at the outset of the intervention and any of the groups decrease in attendance to only two people, the two groups will be combined to form one group that will meet for the remaining weeks of the intervention period.

The group sessions will be led by experienced occupational therapists who have been trained in group theory and facilitation as well behavioral health and fall prevention. The social learning model will be used as the theoretical basis for all groups. Situated learning theory, which is derived from social learning theory, posits that behavior results from interaction between the person and the situation. The learner is placed in contexts (the intervention group and practicing at home) that allow for simulated and actual application to everyday situations, whereas peers enhance the learning experience with feedback. In social situations, individuals gain motivational support from others and access both expertise and collaborative thinking, increasing opportunities to acquire and apply new knowledge. This approach has successfully been used in effectiveness studies with individuals who were homeless,

mentally ill, had an intellectual disability, as well as across a wide age span from 12-79 years of age. Group participants functioning at a variety of levels are likely to benefit from others' experiences of completing the intervention activities and identifying strategies to follow through with recommendations.

The occupational therapist member of the study team will begin each group by reviewing the purpose and reminding participants that they can choose how much to share or not share. The purpose will be described as a forum to share their experiences with the intervention, discuss any falls during the week and identify strategies to address any challenges. The discussion will begin with a quick check in with each group member to provide a structured opportunity for every participant to speak at least once during the group. The check in will be a brief structured question such as, "Identify one exercise you liked doing this week and one that you might have had some difficulty with." This structure gives the participants permission to have challenges with the intervention to help alleviate discomfort or embarrassment with having to initiate this topic. It also ensures that every group member participates verbally should they be less active in the remainder of the discussion. Based on the check in responses, the occupational therapist member of the study team will facilitate a group discussion among participants that encourages them to share strategies and commonalities with each other. Group members find advice from peers to be more valid than from a professional. The occupational therapist member of the study team will use their expertise to ensure the conversation stays on the topic of falls and intervention strategies and to correct any misinformation that might be shared. The therapist will have a list of common topics to interject if the participants exhaust their own concerns or if the group conversation veers off course. Topics will include common issues related to fall prevention such as identifying and removing environmental obstacles, finding time to complete exercise, maintaining good nutrition to support physical health, and how to speak with your doctor about medication side effects such as dizziness, etc. Finally, group time may be spent reviewing exercises if needed. If individuals raise concerns that cannot be addressed in the group due to time or because the topic is beyond the scope of the group, they will be redirected to their individual session or another resource.

Independent Home Exercises: Home based exercises will be tailored to each participant's individual needs and skill sets, which will be determined at the baseline assessment. The general categories of the exercises include air squats, bicep curls, burpees, and single leg stands. Links to the exercises can be found below. Participants will complete assigned exercises on their own at home and will be instructed to record the exercises they complete on the Home Exercise Form, which is a tool for personal use by the participant and will not be returned to the study team. The exercise assignments will take about 30 - 60 minutes to complete per time the participant exercises. During the first virtual group sessions, an occupational therapist member of the study team will describe and demonstrate the assigned exercises. Participants may use this time to ask questions about the exercises. Further, if a participant was unable to attend the first virtual group session, the assigned exercises will be demonstrated by an occupational therapist member of the study team during the first phone check-in. In the case that assigned exercises will be demonstrated at the first phone check-in, the phone check-in will occur using Zoom instead of phone call.

Participants will be able to refer back to video demonstrations of the assigned exercises on a YouTube channel called "Boston ARCH Home Exercises". The YouTube channel will include videos of occupational therapist members of the study team demonstrating the assigned exercises. The videos on the YouTube channel will remain at a visibility status of "unlisted", which means they can only be accessed by a URL. Comments on the videos have been disabled. Study staff will provide participants with the limited access URLs at the first virtual group session, phone check-in, or by email upon participant request. Participants will be encouraged to keep the limited access URLs private and not share the links with people outside of the study.

URLs:

https://youtu.be/BGR69rKSMCA https://youtu.be/mfrOBDuRP7M https://youtu.be/2IeSb2UXsm4 https://youtu.be/3ypbuWluf3M

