4.2.2 Secondary Outcome Measures

There are also several secondary outcome measures:

- Falls from participant self report, defined as an unexpected event, including a slip or a trip, in which a participant lost their balance and landed on the floor, ground, or lower level, or hit an object like a table or a chair.
- Physical Function measured using the Short Physical Performance Battery assessment
- Frailty phenotype¹⁵, which includes measures of exhaustion, low activity, weight loss, slowed walking, weak grip.
- Alcohol and other drug use from self report measured using the validated Addiction Severity Index (ASI)¹⁶⁻¹⁸
- 5 Study Design

The Boston ARCH 4F Fall Prevention Pilot is a sub-study of the Boston ARCH 4F Study, a longitudinal cohort study of 251 HIV infected men and women who have a spectrum of alcohol and other drug use. The Boston ARCH 4F study aim is to examine the association between alcohol use and falls and fractures and whether frailty mediates these associations in people living with HIV (PLWH). The Fall Prevention Pilot will recruit participants from the Boston ARCH 4F Study to test the acceptability and feasibility of a randomized trial of a 10-week virtual intervention to reduce fall risk PLWH who consume alcohol.

Eligible cohort participants with an elevated risk for falls will be randomized to either the intervention or control (usual care plus educational brochure).

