8.9 Individual Check-In via Phone Call

The phone check-in will occur between the first and second weekly virtual group sessions, and follow-up check-ins will occur once weekly after the initial check-in for the entirety of the intervention period, for a total of 10 weekly check-in calls. These phone calls will be conducted with an occupational therapist member of the study team. As the study's primary aim is to assess acceptability and feasibility, there is no set limit of missed weekly check-ins that triggers dropping participant from the study. If a participant stops participating in weekly exercises, the occupational therapist conducting the weekly check in with the participant will inquire as to the reasons why the participant stopped completing the exercises. This feedback will be used to modify the exercises going forward (e.g., frequency, intensity). Additionally, individualized reminders (e.g. phone alarm, calendar update) for the various intervention components will be set during the individual check-ins.

Post-Study Assessment- After the 10 week intervention is complete, all randomized participants (intervention and control groups) will be asked to complete a post-study interview (a series of questionnaires to assess fall history and efficacy, substance use, prescription medications, physical and social environment, food security, and frailty) and physical assessments (physical function measures including grip strength, short physical performance battery, and vision acuity) in-person at BUMC with an RA or RC. Additionally, an occupational therapist member of the research team will conduct the Canadian Occupational Performance Measure. The post-study assessment will take approximately 2 hours to complete. The RAs and RC will reach out to participants approximately 8-9 weeks after randomization to schedule the post-study assessment, and the post-study assessment will be completed approximately 10 weeks (up to 14 weeks) after randomization.

9 Informed Consent

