To describe acceptance of the intervention among those randomized to intervention, mean and 95% confidence intervals will be provided for the number of sessions attended and overall satisfaction with the intervention. Compliance with the study protocol will be described the percent and 95% confidence of participants completing the study follow-up evaluation (of all participants). Estimates of intervention effects will be described through odds ratios and 95% confidence intervals for any falls during the intervention period, using logistic regression to control for baseline fall history. Mean differences and 95% confidence intervals for physical function score at the end of the study period, controlling for baseline physical function score, will be estimated through linear regression models.

14. Literature References

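### Falls are prompted weekly in the intervention arm but not asked about in the control arm until the end visit, so unequal recall may bias the any-fall odds ratio

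*Combined protocol and SAP*

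**What the plan says.** **Outcome.** Falls are a secondary outcome: "Falls from participant self report, defined as an unexpected event, including a slip or a trip" (section 4.2.2). The definition goes on to require that balance was lost and that the person ended up on a lower surface or struck an object.

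**When it is measured.** Section 5 places the standardized assessments at baseline and trial completion only. The post-study interview in section 8.9 is "a series of questionnaires to assess fall history and efficacy, substance use, prescription medications" and other domains, held about 10 and up to 14 weeks after randomization.

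**How it is analysed.** Section 13 plans "odds ratios and 95% confidence intervals for any falls during the intervention period, using logistic regression to control for baseline fall history".

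**Intervention arm.** Each weekly group is introduced as a forum to "discuss any falls during the week and identify strategies to address any challenges", with the therapist "reminding participants that they can choose how much to share or not share" (section 8.8). Section 8.9 adds individual calls, "for a total of 10 weekly check-in calls". Section 6.2 says experiences with falls may be discussed on these calls.

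**Control arm.** Controls get an assignment call with a brief overview of the fall and alcohol materials, then the materials: "The educational materials will only be mailed once, unless the participant misplaces the educational materials" and asks for another copy (section 8.7; section 8.5 agrees). Both arms have a scheduling contact at about 8-9 weeks (section 8.9).

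No section describes a fall diary, calendar or interim fall question given to both arms. The only participant log, the Home Exercise Form, records exercises and is not returned (section 8.8).

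**The concern.** A self-reported event recalled over 10 to 14 weeks depends on what has kept it in mind. One arm has a recurring occasion to name and discuss falls. The other must recall the period with no intermediate question. If the share of true fallers who report a fall differs between arms, the odds ratio shifts even when the intervention does nothing, and a real benefit can be hidden or exaggerated.

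Adjusting for baseline fall history does not help, because the difference in prompting arises after randomization. Masking does not help either. Section 12.1 conceals allocation only until assignment, no masking of the end interview is described, and the research assistants and coordinator who tell controls their assignment also run the post-study visit.

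At stake are the preliminary estimates of falls outcomes that section 13 names as a goal, including the control-arm fall rate. Sessions attended and satisfaction, the primary outcomes, are not touched.

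**Working it through.** **1. The plan's own figure.** Section 13 gives no figure for the fall odds ratio or for recall. Its only power statement is a Cohen's d of 1.0 for 80% power with 80% follow-up. With 0.8 × 20 = 16 per arm and two-sided alpha 0.05 (assumed; not stated), the normal approximation is Φ(1.0 × √(16/2) − 1.96) = Φ(0.868) = 80.7%. The noncentral t gives 78.1%. The figure reproduces and fixes 16 per arm as the planning number.

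**2. Prompting about falls between randomization and the end visit.**

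| | Intervention | Control |
|---|---|---|
| Group forum that names falls | weekly, 10 weeks | none |
| Therapist calls where falls may be discussed | 10 | none |
| Fall-prevention materials | not described | one set, by mail or email |
| Described contact asking about own falls | invited weekly | none |
| Common diary or calendar | none | none |

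**3. Illustration of size.** Let p be the true any-fall risk (equal in both arms, so no true effect) and s the share of true fallers who report a fall, with no false reports. Then

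observed OR = [s_I·p / (1 − s_I·p)] ÷ [s_C·p / (1 − s_C·p)].

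Assumed, not from the documents: s_I = 0.95; s_C = 0.75 or 0.85; p = 15%, 25%, 35%.

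| True risk | s_C = 0.85 | s_C = 0.75 |
|---|---|---|
| 15% | 1.14 | 1.31 |
| 25% | 1.15 | 1.35 |
| 35% | 1.18 | 1.40 |

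Worked case, p = 25%, s_C = 0.75: (0.2375/0.7625) ÷ (0.1875/0.8125) = 0.3115 ÷ 0.2308 = 1.35. The control fall rate would be seen as 18.75% instead of 25%.

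**4. Sensitivity to the risk.** The only fall rate in the documents is up to a third per year in middle-aged people with HIV (section 3.1). At constant hazard that is 1 − (2/3)^(10/52) = 7.5% over 10 weeks and 10.3% over 14. This sample is selected for fall risk, so higher values are plausible. At p = 10% the formula still gives 1.13 and 1.29. The assumed reporting gap drives the result more than the risk does.

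**5. With a true benefit.** True OR 0.70 and control risk 25%: intervention odds 0.3333 × 0.70 = 0.2333, risk 18.9%, reported 0.95 × 18.9% = 18.0%, odds 0.219. Dividing by the reported control odds gives 0.219/0.270 = 0.81 (s_C = 0.85) or 0.219/0.231 = 0.95 (s_C = 0.75).

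**6. The other direction.** If the intervention arm under-reports by the same amounts, the null results are the reciprocals: 1/1.14 = 0.88 down to 1/1.40 = 0.71.

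**7. Scale of random error.** With 16 per arm and equal risks, SE of log OR = √(2/(16·p·(1 − p))). At p = 25% this is √(2/3) = 0.816, so the unadjusted 95% interval spans a factor of exp(1.96 × 0.816) ≈ 5.0 either side. Over 35% to 15% risk the factor runs from 4.3 to 7.0.

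**The case against.** A reader might infer more than the text supports, and the counter-case has force on several points.

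- *Every intervention participant reviews their falls weekly.* Not established. Sharing is optional, the example check-in question is about exercises, groups last about 30 minutes, and sessions can be missed. The calls are set up for questions, exercise feedback and reminders; no fall question is prescribed.
- *Controls have no exposure to the topic.* Wrong. They receive fall-prevention materials with an overview call. Both arms also had fall-risk screening and a baseline fall history, and come from a cohort already asked about falls. What controls lack is any contact that asks about falls between randomization and the end visit.
- *Trivial slips and trips count.* They do not, unless balance is lost with a landing or impact. Such events are less forgettable, and any-fall status needs only one to be recalled.
- *The bias must run against the intervention.* Not shown. Unmasked participants who have worked with a therapist for 10 weeks may wish to appear improved.
- *The large trial will be planned on a distorted effect.* No section commits to sizing a trial from this odds ratio.

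It is also fair that the comparison is declared unpowered and that random error far exceeds the illustrated shift. But a wide interval conveys imprecision. It does not tell a reader that the estimate may be displaced, or that the control rate may be under-counted.

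After all this, the unequal prompting itself still stands, and nothing in the plan offsets it.

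**Conclusion.** The plan prompts recall of falls in one arm and not in the other, for an outcome that rests on self-report at a single end visit. The any-fall odds ratio may therefore be biased. That unequal recall will occur, and in which direction, cannot be settled from the documents. Fuller intervention-arm recall would raise the odds ratio, and a wish to please would lower it.

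The size is unknown. The 1.14 to 1.40 range is an illustration resting wholly on assumed reporting of 95% against 75-85%, true risks of 15-35%, no true effect and no false reports. The pilot could not detect a shift of that order, given an interval factor of 4.3 to 7.0 either side.

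This is a cheap improvement to an unpowered, descriptive secondary analysis. It is not a flaw in the primary feasibility and acceptability outcomes. It is worth making because section 13 sets out to obtain preliminary estimates of falls outcomes.

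**What to change.** Give both arms the same one-page weekly fall calendar at assignment, carrying the section 4.2.2 definition and sent by mail or email on the same schedule. Ask all participants to bring it to the post-study visit, and use it there as the recall aid for the fall question. Report calendar return by arm. State in section 13 that residual differential recall remains a limitation of the fall odds ratio.

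The cost is one page for about 40 people and a minor amendment; the mail and email channels already exist for controls, and the analysis model is unchanged. Calendar return is itself useful feasibility information.

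The downsides are slightly raised fall awareness in controls, whose condition is otherwise usual care plus a brochure, and some calendars not returned, possibly unequally because the intervention arm has more staff contact. The calendar would lessen the imbalance, not remove it, which is why the limitation should be stated as well.
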